8.5 Site-level Poolability

At the final analysis, poolability of data from multiple sites will be verified by examining the primary safety and effectiveness endpoints using logistic regression models. Site-level poolability will be considered appropriate provided that these measures are similar among sites.

It is expected that some sites may have too few patients to provide reasonable site-level estimates of the primary measures. Each investigative site will be allowed to enroll no more than 20% of the patients in each stratum to ensure the overall results are not biased by the results from a single site. Pooling of this information will be explored based on hospital size (large versus small, determined based on number of beds and annual number of discharges), site enrollment (large versus small), type of hospital (community versus teaching), and other group-wise strategies.

It is recognized that patient baseline characteristics may differ among sites, with some sites routinely treating specific patient types (e.g., trauma patients). It is anticipated that the primary endpoint measures may be related to covariates that reflect this. Thus, observed site-specific differences among the primary endpoints will be checked for

confounding with other measured covariates (e.g., age, sex). This can be accomplished using logistic regression models that include site and other measured covariates as independent variables.

Should one or more sites be found to differ significantly from the rest, then logistic regression analysis will be performed with an intercept term and a covariate to distinguish between the unusual site(s) and those sites that are considered poolable. Analysis on the primary endpoints will be performed by constructing 95% confidence interval on odds ratio for the intercept term.

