8.1.2 Primary Safety Hypothesis

The primary safety endpoint is the rate of 12-month freedom from major adverse events. Major adverse events are defined as: clinical perforation, clinical migration, clinical fracture, embolization of the filter or filter fragments to the heart or lungs, IVC thrombotic occlusion, new symptomatic DVT while a filter is indwelling, access site complications with clinical sequelae, and procedure-/device-related death. The analysis requires that the performance goal of 80% be met for freedom from major adverse events at 12 months. The performance goal was derived based on what are considered clinically acceptable rates for each complication in the overall population.⁴⁸

The null (H_0) and alternative (H_A) hypotheses are expressed as follows:

$$H_0: S(t) \leq 80\%$$

$$H_a: S(t) > 80\%$$

where:

- t is time through 12 months
- $S(t)$ is the true rate of freedom from major adverse events at time t .

The hypothesis will be assessed using a Z-statistic. The Z-statistic is given by

$$Z = (\hat{S}(t) - 0.8)/SE$$

where:

- $\hat{S}(t)$ = Kaplan-Meier estimate of freedom from major adverse events ($S(t)$) at 12 months
- SE = Standard Error = $\sqrt{V(S(t))}$, where $\hat{V}(\hat{S}(t))$ is the estimate of the variance of the Kaplan-Meier estimate using the methods described by Peto et al.⁵⁰

The performance goal will be said to have been met provided the null hypothesis is rejected in favor of the alternative if $\hat{S}(t) - 0.8 > Z_{\alpha}SE$, for $\alpha = 0.025$. The hypothesis will be tested only for patients receiving Celect[®] filters.

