8.3 Sample Size

The study is designed to enroll 320 patients in the Celect[®] filter stratum (to evaluate the safety and effectiveness hypotheses) and up to 150 patients in the Günther Tulip[®] filter stratum at up to 40 sites globally. At least half of the study patients in the Celect[®] filter stratum will be enrolled at US sites.

For the primary effectiveness endpoint, based on what are considered clinically acceptable rates for technical placement success and new symptomatic PE in the overall

population, a performance goal of the rate of technical placement success and 12-month freedom from new symptomatic PE while a filter is indwelling was established to be 90%.⁴⁸ Additionally, based on the data from previous Cook sponsored studies (as summarized in Section 4.0), the rate of technical placement success and 12-month freedom from new symptomatic PE while a filter was indwelling was estimated to be 98.4% for the Celect[®] filter stratum. A sample size of 70 patients will be required to assess the primary effectiveness hypothesis for the Celect[®] filter stratum, with a one-sided exact binomial test, at a type I error rate of 0.025, and a power of 0.9. The calculation was performed with the SAS UnifyPow macro.

For the primary safety endpoint, based on what are considered clinically acceptable rates for each complication in the overall population, a performance goal of the rate of 12-month freedom from major adverse events was established to be 80%.⁴⁸ Based on the data from previous Cook-sponsored studies (as summarized in Section 4.0), the rate of 12-month freedom from major adverse events was estimated to be 92.2% for the Celect[®] filter stratum. A sample size of 88 patients will be required to assess the primary safety hypothesis for the Celect[®] filter stratum, with a one-sided exact binomial test, at a type I error rate of 0.025, and a power of 0.9. The calculation was performed with the SAS UnifyPow macro.

Based on sample size calculations, a minimum of 88 patients in the Celect[®] filter stratum will be required to evaluate the safety and effectiveness endpoints. Cook intends to enroll 320 patients in the Celect[®] filter stratum; this sample size allows for an attrition rate of 72% (i.e., 60% of filters to be retrieved prior to 12 months and an additional 12% of patients who may die, withdraw, or become lost to follow-up). The study may also enroll up to 150 patients in the Günther Tulip[®] filter stratum.

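### The safety poolability check in 8.5 uses logistic regression and, as written, ignores the censoring that the primary Kaplan-Meier analysis handles, so site differences in filter retrieval can pass for safety differences

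*Combined protocol and SAP*

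**What the plan says.** - **The check (8.5).** At the final analysis, "poolability of data from multiple sites will be verified by examining the primary safety and effectiveness endpoints using logistic regression models". Site differences are then examined for confounding, again by logistic regression, with age and sex as the example covariates. If one or more sites still stand out, the primary endpoints are analysed by a logistic model with an intercept and an indicator for the unusual sites, and a confidence interval is formed from the intercept.
- **The endpoint being checked (8.1.2).** The primary safety test is a Z-statistic built on the "Kaplan-Meier estimate of freedom from major adverse events" at 12 months.
- **Expected incompleteness (8.3).** The plan says "this sample size allows for an attrition rate of 72"%, made up of "60% of filters to be retrieved prior to 12 months" and a further 12% for death, withdrawal or loss.
- **What happens after retrieval (1.0, 6.3.2).** Follow-up ends one month after successful retrieval. In that month only access site complications with sequelae and procedure-related death count towards the safety endpoint.
- **Site mix (8.5).** Sites are expected to differ in baseline characteristics, "with some sites routinely treating specific patient types (e.g., trauma patients").
- **General clause (8.2).** Survival methods, with Kaplan-Meier and Cox as examples, are to be brought in where data are censored. Section 8.5 does not repeat this.

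**The concern.** A 12-month event rate with heavy censoring has no natural binary version. To fit a logistic model, the analyst must decide what to do with a patient whose filter came out at, say, month 3 without an event. The two direct choices are to count the patient as event-free or to leave the patient out, and 8.5 does not say which. Either choice puts time at risk into the site effect.

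The plan expects sites to treat different kinds of patient, and section 4.0 describes trauma and perioperative patients as having temporary risk. Retrieval patterns that differ by site are therefore a reasonable inference, though the documents do not state it.

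Two things are at stake. The check can signal a safety difference where none exists, or mask one that does. And a flagged site takes the primary safety endpoint out of the Kaplan-Meier analysis and into a logistic intercept, where the same censoring problem affects the primary result.

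**Working it through.** **1. The plan's own figures.** For safety (goal 80%, expected 92.2%, one-sided exact binomial at 0.025), n = 88 with success at 78 or more event-free gives type I error 0.0238 and power 0.919. Inflation: 88/(1 − 0.72) = 314.3, so 315, against 320 planned; 320 × 0.28 = 89.6. These reproduce. They also show that the plan treats retrieval as attrition.

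**2. Expected odds ratio when the share retrieved differs.** From 8.3: 92.2% event-free at 12 months, 320 patients, 60% retrieved overall. Assumed here: constant hazard, exponential retrieval times independent of risk, follow-up ending at retrieval, two groups of 160, no other loss. With Λ = −ln 0.922 = 0.0812, q the share retrieved by 12 months and M = −ln(1 − q):

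- observed event probability: e = Λ/(Λ + M) × [1 − exp(−(Λ + M))]
- probability of completing 12 months event-free: c = (1 − q) × 0.922

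For q = 85%: M = 1.8971, e = (0.0812/1.9783) × (1 − 0.1383) = 0.0354, c = 0.1383.

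For q = 35%: M = 0.4308, e = (0.0812/0.5120) × (1 − 0.5993) = 0.0636, c = 0.5993.

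Odds ratio for an event, high-retrieval v low-retrieval group:

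- retrieved counted as event-free: (0.0354/0.9646)/(0.0636/0.9364) = 0.0367/0.0679 = 0.54
- retrieved dropped: (0.0354/0.1383)/(0.0636/0.5993) = 0.256/0.106 = 2.41

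The true hazard ratio is 1. For 75% v 45% the same formulas give e = 0.0426 and 0.0590, c = 0.2305 and 0.5071, and odds ratios of 0.71 and 1.59.

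**3. How often this reaches significance.** Simulated trials, likelihood-ratio test at 0.05, no true difference:

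| Setting | Logistic, event-free | Logistic, dropped | Log-rank |
|---|---|---|---|
| 160 v 160, 85% v 35% retrieved | 23% | 31–32% | 5% |
| 160 v 160, 75% v 45% | 11% | 14% | 5% |
| 160 v 160, 85% v 35%, half the hazard at the procedure | 8–9% | 67% | 5% |

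With uniform rather than exponential retrieval times, the two logistic figures are 13% and 51% at 85% v 35%, and 8% and 20% at 75% v 45%.

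**4. A single site.** The enrollment cap allows 20% × 320 = 64 patients at one site. Set that site at 85% against 54% elsewhere, or 35% against 66%, which keeps the overall share at 60%. It is then falsely flagged in roughly 9–14% of trials over both codings. An average site has 320/40 = 8 patients and is flagged in about 1–9%.

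**5. When only the timing differs.** Hold the share at 60% in both groups and move the retrieval month. With event-free coding and retrieval at month 1, the event rate is 0.4 × 0.078 + 0.6 × (1 − 0.922^(1/12)) = 0.0312 + 0.0040 = 3.5%. At month 11 it is 0.0312 + 0.6 × (1 − 0.922^(11/12)) = 0.0312 + 0.0430 = 7.4%. The odds ratio is 0.46. Dropping event-free retrieved patients gives 0.47, in the same direction. Adding 12% other loss, false signals occur in 36% and 29% of runs. At month 3 v 9 they fall to 16% and 13%. With half the hazard at the procedure, the range over all timing settings is 6–12%. The log-rank test stays at 4–5%.

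**The case against.** The strongest reply is that the plan is not silent. Section 8.2 commits to survival methods where there is censoring. The covariate list in 8.5 is open, and time to retrieval is among the study assessments in 1.0, so an analyst could adjust for it before any site is declared unusual. This stands in part: it is wrong to say that the plan cannot handle early retrieval. But 8.2 is general, whereas 8.5 names logistic regression for the check, the confounding step and the follow-on analysis. If retrieved patients were treated as missing, 8.4 would lead to case deletion, which is the dropped coding.

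A second reply concerns size. Two blocks of 160 at 85% v 35% is an extreme contrast, and the trigger in 8.5 is one or more sites, not two halves of the trial. This also stands. Single-site rates are lower, and the results move a good deal with the shape of the hazard, which matters because the endpoint includes procedural events.

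A reader might go further in four ways that the documents do not support:

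- *That sites will look different.* Expected crude rates shift, but at 85% v 35% with constant hazard about 68–77% of trials show no signal.
- *That 60% retrieval is planned.* It is an allowance in the sample size.
- *That the two codings always bias in opposite directions.* They do when the share retrieved differs. When only the timing differs, both point the same way.
- *That the effectiveness check fails as well,* because only about 1.6% × 320 = 5 failures are expected. Section 8.5 already foresees sites too small for their own estimates and turns to hospital groupings, and it specifies no site-by-site significance rule. The primary effectiveness test is itself binary, so the mismatch with Kaplan-Meier does not arise there.

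**Conclusion.** The point holds for safety. Section 8.5 specifies a method without censoring for an endpoint whose primary analysis depends on it, and no other section overrides that choice. The fault lies in the stated method as well as in the missing coding rule.

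The bias is real but its size is uncertain. Under the settings examined, the false-signal rate for grouped sites ranges from about 6% to 67% against a nominal 5%, and is roughly 9–14% for one site at the enrollment cap. These figures rest on assumed retrieval patterns, an assumed hazard shape and one of two codings. The log-rank result near 5% requires retrieval to be independent of risk. If sicker patients keep their filters longer, a censored analysis is affected too.

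The Kaplan-Meier test is untouched unless a site is flagged. If one is, the safety result comes from a logistic intercept with the same weakness. The change should be made before outcome data are reviewed.

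**What to change.** In 8.5, for the primary safety endpoint:

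1. Check poolability by a log-rank test or Cox regression with the same censoring as 8.1.2, across the groupings already listed (hospital size, site enrollment, hospital type) and for the larger sites.
2. Use a Cox model for the covariate check.
3. Add a site frailty term as exploratory only. About 16 to 21 events over up to 40 sites will not support more.
4. Wherever logistic regression is kept for safety, including the unusual-site analysis, state how patients retrieved before 12 months are coded.

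The cost is SAP wording and routine programming, with no new data. The downside is low power for single sites, which the logistic model shares.

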8.1.1 Primary Effectiveness Hypothesis

The primary effectiveness endpoint is the rate of technical placement success and 12-month freedom from new symptomatic PE while a filter is indwelling. The analysis requires that the performance goal of 90% be met for technical placement success and freedom from new symptomatic PE at 12 months while a filter is indwelling. The

performance goal was derived based on what are considered clinically acceptable rates for technical placement success and new symptomatic PE in the overall population.⁴⁸ The performance goal will be said to have been met provided the null hypothesis is rejected in favor of the alternative with a one-tailed exact binomial test at the 0.025 level. The hypothesis will be tested only for patients receiving Celect[®] filters. Given that π is the probability that a randomly selected patient did not experience any technical placement failure or new symptomatic PE within 12 months while a filter is indwelling, the null and alternative hypotheses are as follows.

Null Hypothesis: The rate of technical placement success and 12-month freedom from new symptomatic PE while a filter is indwelling, π , does not meet the performance goal (90%).

$$H_0: \pi \leq 90\%$$

Alternative Hypothesis: The rate of technical placement success and 12-month freedom from new symptomatic PE while a filter is indwelling, π , meets the performance goal (90%).

$$H_a: \pi > 90\%$$

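### Section 8.5 picks out sites from the outcome data with no stated test, level or multiplicity control, then bases the primary-endpoint interval on the sites that remain

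*Combined protocol and SAP*

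**What the plan says.** Section 8.5 (Site-level Poolability) checks the two primary endpoints across sites with logistic regression and accepts pooling if the results are similar. It then gives a rule for when they are not: "Should one or more sites be found to differ significantly from the rest, then logistic regression analysis will be performed with an intercept term". The second element of that model is described as "a covariate to distinguish between the unusual site(s) and those sites that are considered poolable". The primary endpoints are next analysed through a 95% confidence interval on the intercept. No test, significance level, overall heterogeneity gate or multiplicity adjustment is given.

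The same section limits enrolment: "Each investigative site will be allowed to enroll no more than 20% of the patients in each stratum". It expects some sites to be too small for their own estimates, says grouping by hospital size, enrolment or hospital type will be explored, and has site differences checked for confounding by covariates. It sets no minimum site size.

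Section 8.3 gives the scale: "The study is designed to enroll 320 patients in the Celect[®] filter stratum". For the other filter and the number of centres it states ceilings: "up to 150 patients in the Günther Tulip[®] filter stratum at up to 40 sites globally".

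Section 8.1.1 sets the effectiveness criterion: "The analysis requires that the performance goal of 90% be met for technical placement success and freedom from new symptomatic PE at 12 months", judged by "a one-tailed exact binomial test at the 0.025 level". Section 8.1.2 judges safety against 80% with a Kaplan-Meier Z-statistic at one-sided 0.025. Section 8.5 does not say whether the intercept analysis replaces these tests or supplements them.

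**The concern.** The same outcomes first decide which sites are unusual and then supply a rate that leaves those sites out. With few patients per site and high success rates, a site with no failures can hardly look significantly good, whereas a small cluster of failures looks significantly bad. Chance flags then remove mainly poor results, and the rate for the remaining sites is too high. An interval built after that selection does not keep the one-sided 2.5% error that 8.1 fixes. At stake are the reported primary rate and, if the intercept interval decides, the claim that a performance goal was met.

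**Working it through.** **Plan's own figures (8.3).** Exact one-sided binomial tests:
- Safety, n = 88, goal 80%, planning rate 92.2%: success at 78 or more; size 0.0238, power 0.919.
- Effectiveness, n = 70, goal 90%, planning rate 98.4%: success at 68 or more; size 0.0242, power 0.898.
- Enrolment: 88 / (1 - 0.72) = 314.3, against 320 planned.

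These agree with the plan to within rounding. Section 8.5 has no figure of its own to reproduce.

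**What the intercept estimates.** Let F = 1 for a flagged site and 0 otherwise, with logit(p) = b0 + b1·F. The fitted b0 is the log odds of success in the unflagged sites. With e failures among m unflagged patients, b0 = ln((m - e)/e) and SE = sqrt(1/e + 1/(m - e)). Flagged patients enter neither expression.

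**Which sites can be flagged.** Average size at the 40-site ceiling is 320/40 = 8. Two-sided Fisher test, one site against the rest:
- Safety planning rate, 0.078 × 320 ≈ 25 failures: 3 of 8 gives p = 0.018; 0 of 8 gives p = 1.0.
- Effectiveness planning rate, 0.016 × 320 ≈ 5 failures: 2 of 8 gives p = 0.005; 0 of 8 gives p = 1.0.
- Safety at the goal, 0.20 × 320 = 64 failures: 0 of 8 is not significant (p = 0.37), but 0 of 16 is (p = 0.049), as are 0 to 2 of 32.

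With small sites only bad ones can be flagged. With larger sites and more events, good ones can be too.

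**One example.** Suppose there are 23 effectiveness failures in 320, so 297 successes (92.8%). The exact test needs 299, so the goal is missed. The all-site logit interval misses it too: ln(297/23) - 1.96 × 0.2164 = 2.134, below ln(0.9/0.1) = 2.197. Now let one site have 3 of 8 failures (Fisher p = 0.014) and carve it out. That leaves 20 failures in 312 (93.6%), and ln(292/20) - 1.96 × 0.2311 = 2.228, a lower limit of 90.3%. The goal is now met.

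**Simulation.** There are 320 patients, identical true rates at all sites, and binary outcomes without censoring. Each site is tested by Fisher at 0.05 (assumed). Flagged sites leave the intercept, and success means that the lower 95% limit exceeds the goal. If no site is flagged, the exact test on all patients applies. Ranges span separate runs.

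| Sites × patients | Endpoint | Any flag, true rate at goal | Any flag, planning rate | False success at goal |
|---|---|---|---|---|
| 40 × 8 | Effectiveness | 66-67% | 34-36% | 5.8-6.6% |
| 40 × 8 | Safety | 60-61% | 56-57% | 8.7-9.2% |
| 20 × 16 | Effectiveness | 41% | 30-32% | 5.4-5.9% |
| 20 × 16 | Safety | 52% | 37-42% | 6.5-7.3% |
| 10 × 32 | Effectiveness | 29% | 14-15% | 3.9-4.1% |
| 10 × 32 | Safety | 30-32% | 24-28% | 3.2-3.7% |

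The exact test on all 320 patients gives about 2% false success throughout.

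- *Direction.* With 40 × 8, no good site was flagged. For safety at the goal, bad and good flags per trial averaged 0.44 and 0.31 (20 × 16) and 0.22 and 0.15 (10 × 32).
- *Size of shift.* When a carve-out occurs, the reported rate rises on average by about 0.5-1.5 points.
- *Planning rates.* Both goals were met in essentially every simulated trial, with or without the carve-out.
- *Other tests.* With 40 × 8 at the planning rates, a chance-bad site is flagged for effectiveness in about 35% of trials by the likelihood-ratio test, 72-73% by Wald and 93% by score; for safety in 56%, 67% and 78-80%.
- *Minimum size.* If only sites with at least 10 patients are tested, flags fall to 0% for 40 × 8. For 40 unequal sites (largest 64) they are 13-41% at the planning rates.

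**The case against.** A reader might infer that most trials with identical sites would lose a bad site by chance, always in the favourable direction, and so falsely meet a goal. The documents do not support that.

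- The per-site 0.05 test is assumed. Section 8.5 speaks of logistic models and similarity among sites, which would also permit an overall test first.
- Forty sites is a ceiling, and the text on small sites points away from testing forty sites of eight one at a time. Under Fisher, several layouts flag in a minority of trials.
- The direction is one-sided only for small sites.
- Sections 8.1.1 and 8.1.2 tie meeting each goal to the exact binomial test and the Kaplan-Meier Z-test. If those govern regardless, the pass/fail error is untouched.
- A shift of about one point is small beside planning margins of 98.4 - 90 = 8.4 and 92.2 - 80 = 12.2 points.

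All of this stands and limits the claim, but it does not remove it. Grouping is only to be explored and has no cut-off. The covariate check does not correct chance selection. Section 8.5 presents the intercept interval as the analysis of the primary endpoints and does not call it a sensitivity analysis. Type I error is judged at the goal, not at the planning rate.

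**Conclusion.** The concern holds in a limited form. Section 8.5 contains an outcome-driven selection step without a defined criterion, followed by an estimate that leaves out what was selected. Under the assumed per-site Fisher test at 0.05, with 10 to 40 equal sites, a chance flag occurs in about 15-66% of trials. The 3-9% false-success figure, against about 2%, applies only if the intercept interval decides the goal, which the plan leaves open. The expected consequence at the planning rates is a slightly flattering reported rate, not a changed conclusion.

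The figures treat both endpoints as binary and all 320 patients as analysable. The plan allows for 72% attrition and uses Kaplan-Meier for safety, so they indicate scale and are not predictions. This should be corrected, but it does not invalidate the design.

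**What to change.** In 8.5, state that the all-site tests of 8.1.1 (exact binomial) and 8.1.2 (Kaplan-Meier Z) remain the primary analyses whatever the poolability result. Make the flagged-site intercept model a labelled sensitivity analysis, reported beside the all-site rate.

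Examine single sites only after a pre-stated minimum site size or grouping rule, with an exact test and Holm or Bonferroni adjustment at a stated level. The exact test matters. With 40 × 8 at the planning rates, Bonferroni with Fisher flags 0.9% (effectiveness) and 1.8% (safety) of trials, and false success at the goal stays near 2%. Bonferroni with score tests still flags 45% and 24%, and with Wald tests 16% and 6%. An overall chi-square gate alone is not a safe substitute: with 40 unequal sites it still lets flags through in 8-20% of trials at the planning rates.

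A random site effect is not a good replacement for the primary estimate. About 5 expected effectiveness failures cannot support a site variance, and the model would displace the exact test.

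The cost is a few sentences and minor programming. The downside is less power to single out one truly deviant small site, which can still be described.

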8.2 General Statistical Analyses

Statistical analysis will be performed using SAS[®] for Windows[®] (release 9.3 or higher) or other widely accepted statistical software. Clinically-relevant baseline variables will be tabulated by each stratum. Continuous variables will be reported as means and standard deviations unless otherwise noted. Categorical variables will be reported as percent. Unadjusted 95% confidence intervals will be presented for the secondary endpoints, with a footnote specifying that they are unadjusted. Survival analysis techniques such as Kaplan-Meier or Cox Proportional Hazards will be incorporated if censoring of data occurs.

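### If sites differ, section 8.5 redirects the primary analysis to a logistic intercept that is not the all-patient rate, and nothing says the section 8.1 tests still decide

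*Combined protocol and SAP*

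**What the plan says.** Section 8.1 contains the only stated success rules, and both apply to Celect patients at all sites. For effectiveness (8.1.1, goal 90%) the null hypothesis must be "rejected in favor of the alternative with a one-tailed exact binomial test at the 0.025 level". For safety (8.1.2, goal 80%), "The performance goal will be said to have been met provided the null hypothesis is rejected in favor of the alternative if" the 12-month Kaplan-Meier estimate exceeds 0.8 by more than the critical value times its standard error. Neither rule mentions sites or poolability.

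Section 8.5 begins with a general criterion: "Site-level poolability will be considered appropriate provided that these measures are similar among sites". It caps a site's share: "Each investigative site will be allowed to enroll no more than 20% of the patients in each stratum". It then sets a contingency. "Should one or more sites be found to differ significantly from the rest", a logistic model is fitted with an intercept and "a covariate to distinguish between the unusual site(s) and those sites that are considered poolable". The next sentence reads: "Analysis on the primary endpoints will be performed by constructing 95% confidence interval on odds ratio for the intercept term".

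Section 8.5 gives no coding for the covariate, no test or level for declaring a site different, and no value to set the interval against. It does not call the model supportive. No other section says which result decides if 8.1 and 8.5 disagree.

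**The concern.** The sentence in 8.5 is a directive about the primary endpoints. Followed as written, it puts a different quantity in place of the one tested in 8.1, and what triggers the change is the outcome data.

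Under the natural 0/1 coding, with poolable sites as reference, the intercept carries no information from the unusual sites. Those sites are picked out because their results are worse or better than the rest, so removing them moves the estimate in a predictable direction. Section 8.1.1 defines its parameter for a randomly selected patient, which is not the same thing.

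At stake is whether a performance goal is declared met. If the two analyses disagree, the plan leaves a choice between them after the data are seen, and the one-sided 0.025 level is then not protected. Site differences are foreseeable: section 8.5 itself expects some sites to treat particular patient types and expects the endpoints to be related to such covariates.

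**Working it through.** **Plan's own figures.** Section 8.5 states none. The section 8.3 sample sizes, at one-sided 0.025, check as follows:
- Effectiveness, 90% versus 98.4%, n = 70: success at 68 or more, exact level 0.0242, power 0.898.
- Safety, 80% versus 92.2%, n = 88: success at 78 or more, exact level 0.0238, power 0.919.

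These reproduce (effectiveness power is marginally under 0.90) but do not settle the present point.

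**Inputs.** Section 8.3 allows 72% attrition from 320, and 320 × 0.28 = 89.6, so about 90 patients are evaluable under case deletion. The other extreme is 320 complete. The 20% cap gives a largest site of 18 of 90 or 64 of 320.

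**What the intercept is.** With one 0/1 site-group indicator and poolable sites coded 0, the intercept is ln(s/f), where s and f are successes and failures in the poolable sites. Its 95% limits are ln(s/f) ± 1.96 × √(1/s + 1/f), back-transformed to a proportion. As odds, the goals are 0.9/0.1 = 9 and 0.8/0.2 = 4; section 8.5 states neither.

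The coding matters. Take 38/64 successes in the unusual site and 230/256 elsewhere. The intercept corresponds to 89.8% (poolable sites as reference), 59.4% (unusual site as reference) or 78.2% (effect coding). The all-patient rate is 268/320 = 83.75%.

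**Worked reversals** (hypothetical counts, complete outcomes, poolable sites as reference). For safety, Z = (p − 0.8)/√(p(1 − p)/n), to be compared with 1.96.

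| Endpoint | Unusual + poolable | All patients | Section 8.1 result | Poolable odds (95% limits) | As a proportion |
|---|---|---|---|---|---|
| Effectiveness | 15/18 + 71/72 | 86/90 = 95.6% | exact p = 0.047, fails | 71 (9.86–511) | 90.8–99.8%, above 90% |
| Safety | 11/18 + 67/72 | 78/90 = 86.7% | Z = 1.86, fails | 13.4 (5.40–33.2) | 84.4–97.1%, above 80% |
| Safety | 44/64 + 224/256 | 268/320 = 83.75% | Z = 1.82, fails | 7.0 (4.83–10.1) | 82.9–91.0%, above 80% |
| Safety | 62/64 + 210/256 | 272/320 = 85.0% | Z = 2.50, passes | 4.57 (3.32–6.28) | 76.8–86.3%, includes 80% |

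For effectiveness with 90 patients, 87 successes are needed (exact p = 0.017). Fisher p-values for the site difference are 0.024 in the first row, 0.0018 in the second and 0.0015 in the last.

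**False success for safety, by simulation.** There were 10,000 trials per cell with complete outcomes. Each site was compared with the rest by a two-sided Fisher test, at 0.05 or at 0.05 divided by the number of sites (Bonferroni). In a grouped version, sites formed five equal groups, tested at 0.05 or 0.01. If anything was flagged, the lower intercept limit for the unflagged sites was compared with 80%; otherwise the 8.1.2 test was used. The true all-patient rate is 80%. With the cap site at 60%, the others are at (0.8 × 90 − 0.6 × 18)/72 = 85%.

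| Scenario | Unadjusted flag | Bonferroni | Five groups | All-patient Z-test |
|---|---|---|---|---|
| Cap site 60%, 90 evaluable | 14.3–14.6% | 9.5–10.6% | 6.5–11.1% | 3.0–3.5% |
| Cap site 60%, 320 complete | 37–56% | 47–49% | 22–42% | 3.0–3.5% |
| Cap site 70%, 90 evaluable | 6.4–7.2% | 4.5–4.8% | 3.1–5.8% | 3.3–3.9% |
| No site differences, 90 evaluable | 4.9–6.4% | 3.7–4.0% | – | 3.5–4.1% |

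Ranges span the assumed sizes of the other sites and, in the grouped column, the tests and levels. At the planned rates (92.2% and 98.4%), with equal sites and 90 evaluable, the two routes disagree in 0.0–1.2% of trials.

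**The case against.** The strongest reply is that 8.1 already governs. Its rules are unconditional, it fixes the population as Celect patients, and 8.5 names no goal, null hypothesis or success criterion. On that reading 8.5 is a descriptive follow-up. This is a possible inference, but the plan does not state it, and the wording of 8.5 points the other way. Where the plan means an analysis to be optional, as in the last sentence of section 8.4, it says so.

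A second reply is that the false-success rates rest on a rule the plan does not contain. The flag test, its level, the site sizes and the comparison with the goal are all assumptions, and the covariate check in 8.5 was not simulated. That stands: the rates show direction and rough size under stated assumptions. It also stands that an interval above 80% is correct for sites truly at 85%. It is false only as a statement about all patients, which is what 8.1 tests.

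Third, the scenarios are severe. At the planned rates, 11/18 or fewer at one site has probability about 0.0003 for safety, and 15/18 or fewer about 0.003 for effectiveness. The 22–56% figures need complete outcomes in all 320 patients and a site at the full cap that is 25 points worse than the rest. The all-patient Z-test itself runs slightly above 2.5%. All of this is right, and it makes the effect conditional.

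Finally, the claim that the intercept describes poolable sites only depends on coding. That is so, but no coding checked returned the all-patient rate.

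**Conclusion.** The point holds, and the text should be corrected. As written, a significant site difference redirects the primary analysis to a quantity that is misnamed, differs from the section 8.1 parameter and, under the natural coding, omits the unusual sites after their results are seen.

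The consequence depends on a true site difference and on the interval being read against the goal. With a cap-size site at 60% and the rest at 85%, false success for safety with 90 evaluable patients is about 6.5–15% across the flag rules tried, against 3.0–3.5% for the all-patient test. With no true differences, a Bonferroni flag adds essentially nothing. With equal sites at the planned rates, the two routes almost always agree.

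Two related gaps are missing detail and carry no weight on their own. The flag has no stated level or multiplicity rule, although up to 40 sites are planned. The binary model in 8.5 is also not reconciled with the Kaplan-Meier censoring in 8.1.2, the case deletion and imputation in 8.4, or the statement in 8.2 that "Survival analysis techniques such as Kaplan-Meier or Cox Proportional Hazards will be incorporated if censoring of data occurs". No section says how a filter retrieved before 12 months enters the 8.5 model.

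**What to change.** Add to section 8.5 a statement that the all-patient Celect tests in 8.1.1 and 8.1.2 alone decide whether each performance goal is met, and that site-adjusted results are sensitivity analyses. Relabel the intercept model accordingly. Alternatively, replace it with an estimate that keeps every site, or with a leave-one-site-out table.

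If the model stays as a sensitivity analysis, call the exponentiated intercept an odds, state the covariate coding and the flag level, and reconcile its handling of patients censored before 12 months with sections 8.2 and 8.4.

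The cost is one or two sentences and a small table. Sample size and alpha do not change. The sponsor gives up an alternative primary analysis that could look more favourable, or less.
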